OBSERVATIONAL STUDY PROTOCOL

Version 1.2 of 02.11.23

TITLE OF THE STUDY

Chronic Postsurgical Pain: Multivariate Prediction Model

ACRONYM OF THE STUDY:

СРоР

Promoter

SIAARTI-Società Italiana di Anestesia Analgesia Rianimazione e Terapia Intensiva (Italian Society of Anesthesia, Analgesia, Intensive Care and Resuscitation)

Coordinating Center

Azienda Ospedaliera Universitaria "Gaetano Martino", Messina

Abstract

Chronic post-surgical pain (CPSP) is a common and disabling postoperative complication; it is defined as pain that develops or increases in intensity after surgery and persists for at least 3 months after surgery.

CPSP syndrome affects millions of people around the world, with an incidence between 10 and 50%. Furthermore, it is considered a serious health but also social and economic problem and represents a significant part of medical prescriptions and healthcare costs. Furthermore, in combination with psychological consequences, chronic pain significantly impairs quality of life and productivity, placing patients at risk of drug addiction.

Several risk factors for CPSP have been established, but the relationship with the characteristics of surgery is unclear, although it is widely associated with iatrogenic nerve damage, and chronicity is linked to remodeling of the central nervous system linked to central sensitization phenomena; a wide interindividual range characterizes the sensation of pain, furthermore, psychological factors such as depression, pain catastrophism, mood, and, stress, could influence pain perception itself. Although surgery is a determining factor in the onset of chronic pain, certain patient characteristics also appear predictive of an increased risk of persistent pain.

Identifying risk factors for CPSP before surgery could help recognize patients at higher risk, using risk prediction models and enabling preventative strategies.

The present study aims to identify the risk factors of CPSP three months after surgery, and, subsequently, develop a risk index to identify high-risk patients considering the multifactorial etiology of CPSP.

A comprehensive item pool was derived from a systematic literature search. Data collection will record parameters at four different times: preoperative assessment (60 to 1 day before the scheduled procedure); evaluation of the perioperative period; and postoperative period (from the third month following surgery).

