The outcome variable is the presence of CPSP assessed 3 months after surgery and defined as an average pain intensity of at least 3 on the NRS scale (11-point one-dimensional pain scale) in the last three days, and pain localized to the surgical field (or in the lesion area) projected into the innervation territory of a nerve located in this area or referred to a dermatome.

Separate prediction models will be developed using data derived from surveys conducted at the relevant time points for the development of the risk index.

The sample size of the development dataset must be large enough to develop a prediction model equation that is reliable when applied to new individuals in the target population. The Authors estimate to include approximately 1500 patients to develop a clinical prediction model of CPSP three months after surgery.

The Authors estimate that at least 10 Centers are needed to enroll the intended study population.

The total expected time, from the date of project approval to the production of the draft manuscript, is 24 months.

Background

Chronic post-surgical pain (CPSP) is a common and disabling postoperative complication; it is defined as pain that develops or increases in intensity after surgery and persists at least 3 months after surgery. It can

be localized in the surgical field, projected into the innervation territory of a nerve located in this area, or referred to a dermatome [1].

CPSP affects millions of individuals worldwide, with an estimated incidence between 10 and 50%, depending on the surgery performed [2]. It is rated serious by 2-10% of patients [2;3]. Furthermore, CPSP is considered a serious medical but also social and economic problem [4;5] and represents a significant portion of medical prescriptions and healthcare costs [6]. Furthermore, in combination with psychological consequences, chronic pain significantly impairs the quality of life [7] and productivity, exposing patients to the risk of drug addiction [8].

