Several risk factors for CPSP have been established [9;10;11]. A wide interindividual range characterizes the sensation of pain; multiple factors influence the perception of pain, such as genetic determinants, neurological diseases affecting the central or peripheral nervous system, inflammatory modulation of tissues, and the presence of inflammatory mediators, as well as the experience of pain [12;13;14;15; 16]. CPSP is widely associated with iatrogenic nerve lesions and chronicity is also linked to the remodeling of the central nervous system which determines central sensitization phenomena [17;18]. Furthermore, psychological factors such as depression, pain catastrophizing, mood, and stress could influence the perception of pain [19;20;21;22].

Although surgery is a determining factor in the onset of chronic pain, some patient characteristics also appear to be predictive of an increased risk of persistent pain: young age [23], female sex [24], preoperative pain [25], high levels of acute postoperative pain [25] and psychosocial factors [26;27]. The most significant limitations of current awareness in this field are the heterogeneity of study methodology, including assessment of pain timing, different definitions of pain, and the small sample size of most of the previous studies.

Identifying risk factors for CPSP before surgery could help identify high-risk patients using risk prediction models and allocate preventative strategies [28;10]. Identification of risk groups in the patient population is critical to providing individualized pain treatment [29] and may help reduce long-term opioid use.

The present study aims to identify the risk factors of CPSP three months after surgery and, to develop a valid risk index to detect high-risk patients that considers the multifactorial etiology of CPSP.

Aim

The main objective of this multicenter observational study is to estimate the occurrence of CPSP three months after any type of surgery and identify risk factors for the development of a multivariate clinical prediction model of CPSP at three months.

Methods

This is a multicenter, prospective, observational study on adult patients requiring any type of surgical procedure. This study is designed and will be reported according to the STrengthening the Reporting of OBservational studies in Epidemiology (STROBE) statement. Ethics Committee approval is mandatory to begin registration at all recruitment centers.

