The treatments will be performed according to the rules and ethical standards on human experimentation and the Helsinki Declaration of 1964 (further revised in 2013). All study participants will provide written informed consent (including all the information about possible risks and side effects) for participation in the study. Every precaution will be taken to protect patient privacy.

For the development and validation of the prognostic models, the guidelines on prognostic modeling studies of individual participant data and the recommendations of the Transparent Reporting of a multivariable predict model for Individual Prognosis or Diagnosis (TRIPOD) will be followed.

➢ Population
 Inclusion criteria:
 Age ≥18 years
 Patients scheduled for elective surgery
 Exclusion criteria:
 Patients with perceptive (or sensorial) alterations of pain

Patients unable to communicate

Cognitive impairment

Insufficient knowledge of the Italian language.

Data collection

Recruitment is competitive. Each participating Center undertakes to include at least 20 patients in the study. Patients will participate in the study voluntarily and will not receive compensation of any kind from anyone, either directly or indirectly. Competitive enrollment means that being a multicentric research project, the number of patients included by each participating Center may vary depending on the inclusion capacity of each. There is therefore no maximum limit to the number of patients that each Center can include. The inclusion of patients in the study will end as soon as the total number of subjects described by the protocol is reached.

Web-based electronic case report forms (CRFs) will be used to collect data. All data will be anonymous and only the local principal investigator could match patients and reference numbers.

A comprehensive item pool was derived from a systematic literature search.

Data collection will record parameters at four different times:

- preoperative evaluation
- evaluation of the perioperative period (before surgery)
- evaluation of the perioperative period (after surgery)

• postoperative period

As regards the post-operative follow-up (three months after surgery), a telephone or outpatient evaluation is foreseen at the discretion of each center.

Preoperative evaluation (60 to 1 day before the scheduled procedur	e)
• Age	
18-35	
36-55	
≥55	
• Sex	
Female	
Male	
• BMI	
≤18.5 - 24.9	
25 - 29.9	
≥30	

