 Alcohol or substances of abuse (Y/N) (specify the substance) 	
 Previous experience of pain NRS ≥5 for 7 days (Y/N) 	

Preoperative evaluation (60 to 1 day before the scheduled procedure)

Presence of chronic pathologies (Y/N) (if yes, provide the list of medications)
Pharmacological treatments including supplements or nutraceuticals (continuous in the last 3 months)

(Y/N) (if yes, provide the list of drugs)

- Chronic pain (NRS \geq 3 for \geq 3 months) (Y/N)
- Neuropathic pain (Y/N) (assessment via questionnaire)*
- Pain catastrophizing (Y/N) (assessment via questionnaire)*
- Anxiety (Y/N) (assessment via questionnaire)*
- Depression (Y/N) (assessment via questionnaire)*
- Presence of pain in the last three days (NRS ≥3 mean pain intensity in the 24 hours) (Y/N)

*Questionnaires

- Evaluation of neuropathic pain: Douleur Neuropathique en 4 questions (DN-4)
- Pain Catastrophizing: Pain Catastrophizing Scale (PCS)
- Anxiety: General Anxiety Disorder-7 (GAD-7)
- Depression: Beck Depression Inventory (BDI)-II

Evaluation of the perioperative period

Evaluation before surgery

• Site of surgery

Head

Vertebral column

Arms/legs

Chest

Abdomen

Genitourinary system

• Surgical technique

Open surgery

- Minimally invasive surgery
- Robotic surgery
- ERAS (enhanced recovery after surgery) protocol (Y/N)
- Anesthesiologic technique
- **General Anesthesia**
- Spinal Anesthesia
- **Epidural Anesthesia**

Peripheral nerve block

- Preventive/protective analgesia (Y/N)
- Premedication (Y/N)
- OFA opioid-free anesthesia protocol (Y/N)
- Postoperative analgesic prescription (Y/N)

Evaluation after surgery

- Pain NRS score \geq 3 at the end of the surgery (Y/N)
- Presence of pain (NRS \geq 5 average value in the 24 hours) in the region of the operation at rest or during movement after surgery (Y/N)
- Analgesic prescription after surgery

≤12 hours of coverage

13-24 hours of coverage

- ≥ 24 hours of coverage
- Postoperative surgical complications (Y/N)
- Postoperative infectious complications (Y/N)
- Mobilization after surgery ≤6 hours? (Y/N)

Postoperative period (third month after surgery)

• Pain assessment: average pain intensity assessed using a standard NRS scale (the cutoff score will be set at \geq 3 mean pain intensity over the last three days) (Y/N).

• Diagnosis of CPSP (the pain is localized in the surgical field or in the area of the lesion, projected into the innervation territory of a nerve located in this area, or referred to a dermatome) (Y/N)

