- Surgical complications (Y/N)
- Infectious complications related to surgery (Y/N)
- Malignancy (Y/N)

Questionnaires:

• Douleur Neuropathique in 4 questions (DN-4)

Outcome variable

The outcome variable is the presence of CPSP assessed 3 months after surgery and defined as an average pain intensity of at least 3 points on the NRS scale (one-dimensional pain scale - from 0 to 10 points) in the last three days and pain localized to the surgical field (or in the lesion area) projected into the innervation territory of a nerve located in this area, or referred to a dermatome [30;31].

Development of the risk index

Separate prediction models will be developed using data derived from investigations conducted at the relevant time points.

(1) Primary version of the risk index, made up of items derived from a systematic bibliographic search (compilation of the item pool).

(2) In a second phase, the Authors will analyze the associations between each of these indices and the probability of CPSP 3 months after surgery (dichotomous variable), evaluated using logistic regression models.

(3) Items that were found to be significant in the bivariate analyses will then be analyzed multivariately (logistic regression models).

(4) In a fourth step, the Authors will safeguard the results of the multivariate analyses by calculating the area under the ROC curve of the model, and then, the cut-off score for a high risk of developing CPSP will be identified with an optimal compromise between sensitivity and specificity.

(5) Finally, the items that will generate significant predictive factors in the logistic regression analyses will be collected into an index. For each value of this index, the Authors will calculate the proportion of patients who reported CPSP at 3 months after surgery.

Statistical analysis of results

The study population will be described by summarizing the variables collected in each period of evaluation of the subject (preoperative, perioperative before surgery, perioperative after surgery, three months post-operatively after surgery). In particular, the discrete variables will be reported in terms of absolute and relative frequency, and the continuous variables will be summarized via mean and standard deviation or via median and interquartile range, based on the symmetry of each distribution.

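### The outcome omits the new-or-increased condition in the protocol's own definition of CPSP, so persisting preoperative pain can be counted as an event and can inflate the weight given to preoperative pain

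*Combined protocol and SAP*

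**What the plan says.** **Definition.** The Abstract says of CPSP that "it is defined as pain that develops or increases in intensity after surgery and persists for at least 3 months after surgery". The Background repeats it: "it is defined as pain that develops or increases in intensity after surgery and persists at least 3 months after surgery".

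**Outcome.** The Outcome variable section, like the Abstract, has CPSP "defined as an average pain intensity of at least 3 points on the NRS scale" over the last three days, with pain in the surgical or lesion area, a nerve territory or a dermatome. No comparison with the preoperative state is required.

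**Month-3 form.** One yes/no item asks about NRS of 3 or more. A second asks for the diagnosis of CPSP, and its bracketed criterion is location only.

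**Eligibility.** The clinical inclusion criterion is "Patients scheduled for elective surgery". The nearest exclusion concerns altered pain perception, not existing pain.

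**Preoperative items.** Under "Preoperative evaluation (60 to 1 day before the scheduled procedure", the form lists chronic pain (NRS 3 or more for at least 3 months), "Presence of pain in the last three days" at NRS 3 or more, an earlier experience of NRS 5 or more for 7 days, and neuropathic pain. All are yes/no, with no site and no 0-10 score. The after-surgery item, by contrast, places pain "in the region of the operation at rest or during movement after surgery".

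**Use.** The Aim is to "estimate the occurrence of CPSP three months after any type of surgery" and to identify risk factors for a prediction model. Items significant in bivariate analysis go forward, backward elimination at 0.05 follows, and the coefficients set the scores.

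**The concern.** A patient whose painful surgical area still hurts at NRS 3 or more three months later meets the written outcome, even if the pain is unchanged or has fallen. By the Abstract and Background, that patient does not have CPSP.

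The listed items cannot separate the two situations afterwards, because an increase cannot be derived from yes/no answers without a site. A baseline score cannot be collected once surgery is done.

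Three results are exposed: the CPSP label, the occurrence estimate, and the coefficient of preoperative pain with the score derived from it. Bootstrap validation corrects optimism, not a mismatch between outcome and definition.

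**Working it through.** **No figure in the plan covers this point.** The sample sizes (1124, 1799, 1440) do not depend on it. The one planning figure used below is the 12 events per parameter at 10% incidence: 1799 × 0.10 / 15 = 12.0.

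**Direction, by logic.**
1. Without preoperative pain in the surgical area, any month-3 pain there is new, so outcome and definition agree at NRS 3 or more.
2. If pain is unchanged or reduced and still at NRS 3 or more, it was at NRS 3 or more before surgery.
3. The extra events therefore fall among patients with baseline pain. I say *almost only*, because the evaluation may precede surgery by up to 60 days and pain can begin in between.

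**Size, by illustration.** All shares are assumptions; none is in the documents.
- N = 1500 with no loss to follow-up; new or increased pain of NRS 3 or more in 15% overall (225 events).
- *Any preoperative pain* means yes to the chronic-pain item or to the last-three-days item.
- Set A: 30% have surgical-area pain and 20% have pain elsewhere only. Set B: 10% and 30%.
- r = 10%, 20% or 30% of patients with surgical-area pain are added as events.

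Formulas: incidence = 0.15 + (surgical-area share) × r. Risk added in the any-pain group = r × (surgical-area share) / (any-pain share), that is 0.6r in A (0.30/0.50) and 0.25r in B (0.10/0.40). The true odds ratio is the one for new or increased pain.

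| r = 10 / 20 / 30% | Set A | Set B |
|---|---|---|
| Incidence | 18 / 21 / 24% | 16 / 17 / 18% |
| Events in 1500 | 270 / 315 / 360 | 240 / 255 / 270 |
| True OR 1: risk with pain (0.15 without) | 0.21 / 0.27 / 0.33 | 0.175 / 0.20 / 0.225 |
| True OR 1: observed OR | 1.51 / 2.10 / 2.79 | 1.20 / 1.42 / 1.65 |
| True OR 2: risks before addition | 0.1069 vs 0.1931 | 0.1138 vs 0.2043 |
| True OR 2: risk with pain after addition | 0.2531 / 0.3131 / 0.3731 | 0.2293 / 0.2543 / 0.2793 |
| True OR 2: observed OR | 2.83 / 3.81 / 4.97 | 2.32 / 2.66 / 3.02 |

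Scores come from coefficients, so the log scale matters. An OR of 2.32 instead of 2 multiplies the coefficient by ln 2.32 / ln 2 = 1.2; an OR of 4.97 multiplies it by 2.3.

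**If assessors filter out half of these cases.** The lowest case (B, r = 5%) gives 0.1625 vs 0.15, OR 1.10, incidence 15.5%. The highest (A, r = 15%) gives 0.24 vs 0.15, OR 1.79, incidence 19.5%. With a true OR of 2, the same cases give 0.2043 + 0.0125 = 0.2168 (OR 2.16) and 0.1931 + 0.09 = 0.2831 (OR 3.30).

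**Selection.** Normal approximation, two-sided 0.05, at a true OR of 2 and with no extra events. Set A, 750 vs 750: difference 0.0862, null SE 0.0184, alternative SE 0.0183, so power = Φ((0.0862 − 1.96 × 0.0184) / 0.0183) = 99.7%. Set B, 600 vs 900, also gives 99.7%. At a true OR of 1, the extra events would make the item significant in about 86%, over 99% and over 99% of studies (A), or 25%, 71% and 96% (B), instead of 5%.

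**Occurrence.** New or increased pain of NRS 1-2 fits the definition but is not an event. It would offset the extra events exactly if it affected 3 / 6 / 9% of patients (A) or 1 / 2 / 3% (B).

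**The case against.** - **The item asks for a diagnosis of CPSP, and CPSP is defined earlier.** A clinician may apply that definition, and the eCRF itself is not in the documents. This stands: the text shows that persisting pain *can* be counted, not that it always will be. But nothing instructs the filtering. Follow-up is by telephone or outpatient visit at each center's discretion, so practice could differ between centers.
- **The purpose is mainly prediction.** Persisting pain is a legitimate predictor, and the C-statistic is valid for the outcome as written. This also stands. A reader might infer that the index is invalid; the documents do not support that. The harm is to the label and to the interpretation of risk factors.
- **The item would be selected anyway.** A reader might infer from the true-OR-1 figures that preoperative pain enters the index only because old pain persisted. The Background already lists preoperative pain among the likely predictors, and at a true OR of 2 it passes the bivariate step with about 99.7% power without any extra events. What remains is mainly over-weighting. The calculation also covers only the bivariate step and a combined item, whereas the plan tests the items separately and they then compete in backward elimination.
- **Occurrence by preoperative pain is largely recoverable.** The planned comparison of patients with and without CPSP already gives it for each item. Model performance by stratum is not planned.

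**Conclusion.** The mismatch between definition, outcome and month-3 item is real. Relative to CPSP as the protocol defines it, the association of preoperative pain with the outcome, and the score derived from it, can be inflated. The direction follows from the text wherever such pain is counted; the size does not. Under the assumed shares, a true odds ratio of 2 becomes 2.3 to 5.0 and a true odds ratio of 1 becomes 1.2 to 2.8, and less if assessors filter. The main harm is over-weighting and a label that does not match the definition, rather than false selection.

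A reader might also infer that occurrence is overestimated. That does not follow: the omitted condition pushes it up, the NRS floor of 3 pushes it down, and the net bias is unknown.

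**What to change.** Reconcile the definition, the outcome and the month-3 item in one of two ways.

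**Minimum, with no new field.** Keep the outcome, label it *surgical-area pain of NRS at least 3 at 3 months*, and state that it includes persisting preoperative pain. Report occurrence and model performance by the chronic-pain item and by the last-three-days item, with patients answering no to both as supporting evidence. This costs a wording amendment and some extra reporting. The no-to-both subset would hold 750 (A) or 900 (B) of 1500 patients. It would have about 112 or 135 events at a true OR of 1 (750 × 0.15; 900 × 0.15), and about 80 or 102 at a true OR of 2 (750 × 0.1069; 900 × 0.1138). That is 5.3 to 9 per parameter for 15 parameters, against the 12 in the Power analysis. Use it for checking, not for refitting.

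**Option, if CPSP as defined is wanted.** Add *new, or increased relative to before surgery* to the outcome and to the month-3 item. Record site and 0-10 NRS at the planned surgical area at the two existing contacts, with the same averaging window, and pre-specify what rise counts. The costs are:
- a CRF amendment across at least 10 centers;
- fewer events (225 instead of 240 to 360 in the illustration);
- a ceiling effect, since a high baseline leaves little room to rise. For example, assume 20% have pain at 3 months and that scores before and after are independent and uniform on 3-10. The chance of a rise is then 28/64 = 0.4375, and the risk is 0.0875 against 0.20, an OR of 0.38 for surgical-area baseline pain. For any preoperative pain the OR is 0.61 (A) or 0.83 (B). This belongs to the new-or-increased outcome itself, so the coefficient must be read with it in mind.

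**If the CRF changes during enrolment,** use the relabelled existing outcome for the model in the whole cohort, and analyse new-or-increased pain as a secondary outcome in patients with a baseline score.

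### The month-3 outcome records current pain and where it is, but not when it began or whether it persisted, so recent site pain can count as CPSP

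*Combined protocol and SAP*

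**What the plan says.** In the Abstract, CPSP is "pain that develops or increases in intensity after surgery and persists for at least 3 months after surgery". The Background repeats that it "persists at least 3 months after surgery".

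The Outcome variable section makes this operational at three months. CPSP is "defined as an average pain intensity of at least 3 points on the NRS scale", with the score averaged "in the last three days and pain localized to the surgical field (or in the lesion area", an innervation territory or a dermatome. The Abstract gives the same outcome.

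The form for the third month after surgery has two pain items, both yes/no. The first applies the cutoff of 3 to "mean pain intensity over the last three days". The second is "Diagnosis of CPSP (the pain is localized in the surgical field or in the area of the lesion", followed by the nerve-territory and dermatome alternatives. The form also asks about surgical complications, infectious complications and malignancy, and includes the DN-4 questionnaire.

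The Data collection section lists four times: preoperative, perioperative before surgery, perioperative after surgery, and the third month. The month-3 contact is by telephone or in clinic, as each center chooses.

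**The concern.** The definition has a time element that the measurement lacks. Take a patient who was free of pain for weeks and then develops pain in the operated area shortly before the month-3 contact, for example from a late complication. If the three-day mean is 3 or more, that patient meets the outcome as written. Whether the patient has pain that persists in the plan's own sense cannot be determined from the data collected.

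This variable carries the whole study. It is the occurrence named in the Aim, the dependent variable of every logistic model, the basis of the ROC cut-off, and the proportion to be reported for each value of the risk index. The bootstrap planned under Statistical analysis of results corrects for optimism. It does not correct a misclassified outcome.

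The gap cannot be closed reliably afterwards, because onset and course have to be asked of the patient at or near the month-3 contact.

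**Working it through.** The check is mainly textual. Each element of the stated definition is set against the item that could measure it.

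| Element | Month-3 item that measures it |
|---|---|
| Pain is present at three months | Three-day mean NRS of at least 3 |
| Pain is related to the operated area | Location wording in the diagnosis item |
| When the pain began | None |
| Whether it has persisted or recurred since it began | None by its wording; the diagnosis item could carry it only if the assessor adds it |

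Can other data fill the last two rows?

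1. The form completed after surgery records pain at the end of surgery and average 24-hour pain in the operated region. That shows early pain, not what happened afterwards.
2. No assessment is planned between that form and month 3.
3. The month-3 items on complications and malignancy may point to another cause of pain in some patients. They do not date the pain, and the plan gives them no role in the outcome. The DN-4 is likewise given no role in dating it.

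Onset and persistence therefore cannot be rebuilt from other items.

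**Sample size.** The plan's figures do not depend on this point. With the shrinkage criterion n = P / [(S − 1) ln(1 − R²/S)], S = 0.90 (assumed, not stated) and R² = 15% of its maximum:

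- 50% incidence, P = 15: R² = 0.15 × 0.75 = 0.1125, n = 1124, as stated.
- 10% incidence, P = 15: R² = 0.15 × 0.478, about 0.072, n = 1799, as stated (1807 if R² is not rounded).
- 10% incidence, P = 12: n = 1440, as stated (1446 if R² is not rounded).

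**Direction of bias.** Let p be the true proportion with persistent or recurrent pain. Let f be the share of the other patients who have recent site pain meeting the threshold, and m the share of true cases whose three-day mean falls below 3. Then

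counted proportion = p(1 − m) + (1 − p)f, and bias = (1 − p)f − pm.

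The bias is zero when f/m = p/(1 − p), which is 1/9 at p = 10% and 1 at p = 50%. The documents give neither f nor m. Purely as an assumption, take f = 1–5% and m = 5–20%:

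- p = 10%: lowest 0.10 × 0.80 + 0.90 × 0.01 = 8.9%; highest 0.10 × 0.95 + 0.90 × 0.05 = 14.0%.
- p = 50%: lowest 0.50 × 0.80 + 0.50 × 0.01 = 40.5%; highest 0.50 × 0.95 + 0.50 × 0.05 = 50.0%.

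At 10% the counted proportion can fall on either side of the truth. These figures show only that the sign is undetermined; they do not estimate the error. The term m also counts as error only if persistence is meant to include pain that comes and goes.

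**The case against.** The strongest reply is that persisting for three months can mean still present at the three-month point, which a month-3 assessment does test. The documents never require uninterrupted pain from the day of surgery. This stands, and it rules out calling the text a flat contradiction. It does not settle the point: even on that reading, pain that began last week has not persisted from anything, and the form cannot tell it apart.

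A second reply is that the diagnosis item names a condition that the protocol defines with persistence, so an assessor may apply the full definition. That is possible. But the item's description covers location only and no instruction asks for more. With at least 10 centers and a choice of telephone or clinic, uniform practice cannot be assumed.

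Three stronger readings are tempting, and the documents do not support them.

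- A reader might infer that chronic means three months for the preoperative chronic-pain predictor but only three days for the outcome. Three days is the recall window for averaging intensity; the outcome's time anchor is the operation and the month-3 assessment.
- A reader might infer that the occurrence will be overstated by a definite amount. No rate is given, and missed recurrent pain acts in the opposite direction.
- A reader might infer that predictor associations, above all with acute postoperative pain, will be weakened. Nothing in the documents establishes that.

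**Conclusion.** The point holds as a gap in measurement. The plan defines CPSP with a persistence element, then collects no information on onset or persistence and has no intermediate assessment to supply it. As written, recent site pain with a three-day mean of 3 or more is counted as CPSP unless assessors add a condition that the form does not state.

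The number of patients affected is unknown, and so is the sign of the net bias in the occurrence. Opposite errors could partly cancel in the occurrence while still misclassifying individual patients in the models. The conclusion rests on the item descriptions in the protocol being what the electronic form asks, with no separate assessor guidance. The model can still be built. What is unclear is whether it predicts CPSP as defined or current pain in the operated area.

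**What to change.** 1. Add one item to the month-3 form, asked of all patients: when did the pain in the operated area begin, and has it been present, continuously or on and off, since then?
2. State in the Abstract and the Outcome variable section how persistence is applied to the outcome. The wording should allow for pain that developed after the operation, since the definition includes pain that develops later; requiring pain from the day of surgery could exclude it. If persistence is not to be applied, or the item cannot be added, call the outcome current pain in the operated area at three months.
3. Report the occurrence and the final model with and without the persistence condition.

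Asking patients below NRS 3 as well allows recurrent pain in a quiet spell to be described. It does not bring those patients into the outcome, because the three-day intensity threshold still excludes them.

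The cost is one field, a sentence in two places, some recall error and possibly fewer events under the stricter definition. On the last, at 10% incidence 1500 patients give 150 events, or 150/12 = 12.5 per parameter for the 12-parameter model. The plan's 1440 implies 144/12 = 12. The slack is small if the 10% refers to the outcome as now written, which is a reason to report both versions.
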